11.2 Imaging protocol

- ^{18}F -FPIA PET/MRI imaging will be carried out at the Hammersmith Hospital site (within Imanova Limited, [name])
- A peripheral venous cannula will be inserted within the arm for radiotracer and MRI contrast injections.
- An arterial cannula will be inserted in the radial artery prior to the start of the scan (after an Allens' test to ensure satisfactory ulnar circulation) under local anaesthetic to allow arterial blood sampling during the scan. Continuous arterial blood sampling at 5mL/min will be performed for the first 10 minutes. Discrete blood samples from baseline to 60 minutes post administration will also be taken for analysis of ^{18}F metabolites. The total blood volume required for all analyses in the study will not exceed 200ml. ^{18}F activity will be measured using a gamma counter according to the working instructions at the site. Volumes will be adjusted to avoid counter saturation.
- Simultaneous ^{18}F -FPIA PET and MRI whole brain imaging (vertex to C1 vertebral body) will be performed.
- Following completion of imaging venous and Arterial cannulae will be removed at the end of the scan and patient will be discharged.
- The patient will be contacted via telephone 24 hours following radiotracer injection, to enquire about any adverse health problems following the scan.

11.3 PET Protocol

- For the PET scan, a maximum of 370 MBq ^{18}F -FPIA will be injected followed by a saline flush.
- PET data will be acquired as a single-bed position dynamic imaging scan of approximately 66 minutes
- Discrete arterial samples totalling no more than 200 ml for metabolite analysis and activity counting will be taken during the scan.

11.4 MRI Protocol

The MRI protocol will include the following sequences:

- Sequences for attenuation correction of PET data (DIXON, zero-TE)
- Volumetric T1-weighted images, pre- and post-contrast administration
- Volumetric T2
- Dynamic susceptibility contrast perfusion (DSC)
- Dynamic contrast enhanced perfusion (DCE)

The exact image acquisition parameters for sequences (e.g. TE, TR, flip angle) are hardware dependent and vary between scanner manufacturers and models, and are therefore not specified here. DWI sequences will be acquired prior to contrast agent administration.

11.5 Radiation Dosimetry

Table 2. Radiation dose estimation:

Tracer	^{18}F -FPIA PET
Maximum ^{18}F -FPIA injected activity per visit	370 MBq
Conversion factor (mSv/MBq)	0.0187
Total effective dose (mSv)/patient	6.9 mSv

In aggregate, the total effective dose for each patient in this study is 6.9 mSv. There is no ionizing radiation from the MR component of the study.

11.6 Data Analysis

Raw PET dynamic attenuation corrected images will be reconstructed. Decay corrected images will then be viewed using Analyze[®], Hermes or other appropriate software. Next, the summed images from 15 min to 65 min will be obtained and regions of interest (ROI) will be drawn around the tumour and normal tissues to derive semi-quantitative uptake parameters: SUV (standardized uptake value) normalised to body weight (bw). The average and maximum SUV at 60 min (SUV_{60,av}, and SUV_{60,max}) will be calculated. Arterial blood samples counted for tracer activity and metabolites of ^{18}F -FPIA will be used to generate the blood input function used to derive the uptake tracer parameters (image derived input function *Measuring fatty acid oxidation in gliomas using ^{18}F -FPIA Version 1.0_01/02/2018 IRAS: 228245*

will also be used).

11.7 Metabolite analysis

The discrete arterial samples taken during the scan will be analysed. Total blood radioactivity will be measured by gamma counting and plasma ^{18}F -FPIA parent fraction will be determined by reverse-phase high-performance liquid chromatography with radiochemical detection.

11.8 Kinetic analysis

The kinetics of ^{18}F -FPIA will be estimated from spectral analysis-derived unit impulse response function (IRF) and Patlak analysis-derived net irreversible plasma to tumour transfer constant (K_i , ml of plasma·s $^{-1}$ ·ml tissue $^{-1}$), as well as compartmental analysis-derived ^{18}F -FPIA delivery (K_1 , ml of plasma·s $^{-1}$ ·ml tissue $^{-1}$) and retention (k_3 , ml of plasma·s $^{-1}$). For comparison, tracer retention will also be estimated from SUV analysis (ratio of SUV at 60 min relative to 5 min).

11.9 Tissue Analysis

All patients enrolled into the study, will have their routine biopsy or surgery tissue made available for analysis. We will seek data from routine clinical tissue assays including MGMT, IDH-1 status used for confirming tumour grade.

Following this we will perform our own analysis on tissue including gene, protein, and phospho-protein analysis. Illumina RNA Seq method or similar will be used for gene expression analysis. An automated reverse-phase protein array (RPPA) platform offering detection of approximately 150-170 protein and phospho-proteins from the major cell proliferation and survival pathways (including phospho-ERK 1/2, GYS1-pSer641) will be employed for protein/phospho-protein analysis. Tumour tissue will be obtained for NMR and Mass Spectrometry metabolomics at the Imperial College Biomedical Research Centre (BRC) Clinical Phenome Centre.

11.10 MRI analysis

MRI structural imaging sequences will be used for motion correction of PET data and to define tumour volumes using semi-automated intensity based segmentation algorithms such as those available in the software 'Jim'. Perfusion data will be analysed using custom in-house image analysis tools and other software tools such as MATLAB, FSL, Nordic Neurolab and Tarquin. MRI and PET imaging

parameters will be combined to develop novel biomarkers which can be used for tumour characterisation and assessment of treatment response.

12. COMPLICATIONS AND RADIATION DOSE

12.1 Complications

There are no immediate complications anticipated of the PET/MRI scan except for a potential mild bruising at the site of insertion of the peripheral cannulas which should resolve in 1-2 weeks. Scans will be stopped at any time during the procedure if the subject is unable to tolerate it.

12.2 Radiation dose

The total effective dose (ED) received from the PET/MRI scan is estimated to be 6.9 mSv. This is similar to the exposure to naturally occurring background radiation for the general population of the UK over a period of 3 years. This exposure should be seen in context of the patients in this study being repeatedly exposed to radiation from X-rays, CT scans and radiotherapy as part of routine care.

12.3 Treatment of subjects

The investigators are responsible for ensuring that deliveries of the tracer and study material are correctly received, recorded, handled and stored safely and properly, in accordance with regulatory guidelines (ICH-GCP and Good Manufacturing Practice (GMP) and used in accordance with this protocol.

13. ADVERSE EVENTS

13.1 Definitions

Adverse Event (AE) **Adverse Event (AE):** any untoward medical occurrence in a patient or clinical study subject.

Serious Adverse Event (SAE): any serious adverse event that:

- **Results in death**
- **Is life-threatening** – refers to an event in which the subject was at risk of death at the time of the event; it does not refer to an event which hypothetically might have caused death if it were more severe
- **Requires hospitalization or prolongation of existing inpatients' hospitalization.**
- **Results in persistent or significant disability or incapacity**
- **Is a congenital anomaly or birth defect**

Medical judgement should be exercised in deciding whether an AE is serious in other situations. Important AEs that are not immediately life-threatening or do not result in death or hospitalisation but may jeopardise the subject or may require intervention to prevent one of the other outcomes listed in the definition above, should also be considered serious.

13.2 Reporting Procedures

All adverse events up to 24 hours post study tracer injection should be reported. Depending on the nature of the event the reporting procedures below should be followed. Any questions concerning adverse event reporting should be directed to the Chief Investigator in the first instance.

13.3 Non serious AEs

All such events, whether expected or not, should be recorded.

13.4 Serious AEs

An SAE form should be completed and faxed to the Chief Investigator within 24 hours. However, relapse and death due to a pre-existing condition, and hospitalisations for elective treatment of a pre-existing condition do not need reporting as SAEs.

All SAEs should be reported to the Research Ethics Committee where in the opinion of the Chief Investigator, the event was:

- 'related', i.e. resulted from the administration of any of the research procedures; and
- 'unexpected', i.e. an event that is not listed in the protocol as an expected occurrence

Reports of related and unexpected SAEs should be submitted within 15 days of the Chief Investigator becoming aware of the event, using the NRES SAE form for non- IMP studies. The Chief Investigator must also notify the Sponsor of all SAEs. Local investigators should report any SAEs as required by their Local Research Ethics Committee, Sponsor and/or Research & Development Office.

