4. RATIONALE FOR CURRENT STUDY

4.1 Aim:

The aim of this study is to quantify the degree of early step fatty acid oxidation in gliomas as imaged by ^{18}F -FPIA PET/MRI.

4.2 Hypothesis:

We hypothesise that FPIA uptake will be higher in high-grade gliomas compared to lower grade gliomas, in keeping with a higher propensity of high grade tumours to generate ATP and NADPH via fatty acid oxidation under bioenergetic stress.

4.3 Statistical Design:

The study is an Observational Non-randomised Phase 2 study to determine the magnitude of the early steps of fatty acid oxidation in glioma using ^{18}F -FPIA PET/MRI. This is the first time we are using FPIA in patients (with glioma), thus we do not know *a priori* the magnitude of uptake. Statistical tests will use a 0.05 significance level and will be 2-sided unless otherwise noted. 10 evaluable patients will be recruited for the study with the Upper Confidence Interval of sensitivity to detect fatty acid metabolism set to $\geq 90\%$. All patients will undergo surgical resection or biopsy for histological confirmation of tumour grade.

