7.1 Study Design

10 evaluable patients with suspected cerebral glioma on previous MRI who are due to undergo surgical resection or biopsy will be enrolled into the study. The patients invited to participate in the study will provide full consent, but will only undergo ¹⁸F-FPIA PET/MRI imaging once they have satisfied the inclusion and exclusion criteria in section 8. Once these have been satisfied, eligible patients will proceed to ¹⁸F-FPIA PET/MRI.

On the day of imaging the patients will undergo a blood test to measure plasma concentrations of carnitine. During the scan, a single dose of ¹⁸F-FPIA (maximum, 370 MBq) IV will be administered to the participant followed by a whole brain dynamic PET/MRI scan over 66 minutes. During the MRI sequences, the patient will receive an additional IV bolus of Gadolinium contrast medium administered through a peripheral venous cannula. Arterial blood sampling through a peripheral arterial line will be performed to determine the concentration of radiotracer within arterial plasma. All the patients that are enrolled into the study will undergo biopsy or surgical resection as part of their routine clinical care, from which their tumour grade will be confirmed; we will obtain tissue from these procedures to perform metabolomics, genomics and proteomics. Surgery or biopsy will be performed typically within 2 weeks but no later than 3 months'. In anticipation of any transformation whilst patients are awaiting surgery, we will record the exact time between imaging and surgery for each patient.

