8. ELIGIBILITY

8.1 Inclusion Criteria:

Patients with radiological evidence of suspected cerebral glioma due for surgery or biopsy and with the following characteristics will be recruited:

1. Age ≥ 18
2. Tumour size at least 2 cm.
3. WHO performance status 0 – 2.
4. If female, the subject is either post-menopausal (at least 1 year), or surgically sterilized (has had a documented bilateral oophorectomy and/or documented hysterectomy for at least 2 years), or if of childbearing potential, must have a negative urine beta human chorionic

- gonadotropin (β -HCG) pregnancy test done at initial screening and on the day of tracer administration. The result of the pregnancy test must be known before administration of ^{18}F -FPIA injection.
5. The subject is able and willing to comply with study procedures, and signed and dated informed consent is obtained.
 6. The subject has a satisfactory medical history as judged by the investigator with no significant co-morbidities, physical examination, and vital signs findings during the screening period (from 21 days before administration).
 7. The subject's clinical and laboratory tests are within normal limits and/or considered clinically insignificant.

8.2 Exclusion Criteria:

1. The subject has received any chemotherapy, immunotherapy, biologic therapy or investigational therapy within 14 days or five half-lives of a drug (whichever is longer) prior to the first dose of ^{18}F -FPIA injection. The subject is pregnant or lactating.
2. The subject is diabetic or has uncontrolled blood glucose or blood lipid levels (clinical decision by investigator), any other chronic illness that will preclude brief discontinuation of medication, or musculoskeletal condition that would not allow comfortable performance of a 66-minute scan.
3. The subject has received, or is scheduled to receive, another IMP/radioactive tracer 1 month before administration of ^{18}F -FPIA injection.
4. Anticoagulation therapy, prolonged prothrombin time, abnormal Allen's test.
5. Unsatisfactory renal function (eGFR<60)
6. The subject has non-MRI compatible devices (a pacemaker, an implantable cardioverter-defibrillator (ICD), a nerve stimulator, a cochlea implant and a drug pump) or implanted material (e.g. non-MRI compatible sternal wires, biostimulators, metals or alloys).

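### A death within 24 hours of the tracer that is put down to the glioma is exempt from SAE reporting, and nobody is named to check that attribution

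*Combined protocol and SAP*

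**What the plan says.** Section 13.1 lists "Results in death" among the criteria for a serious adverse event, with no exception by cause. Section 13.2 sets the window: "All adverse events up to 24 hours post study tracer injection should be reported". It then points to the procedures that follow. Section 13.3 requires non-serious events to be recorded. Section 13.4 opens the serious route with "An SAE form should be completed and faxed to the Chief Investigator within 24 hours" and at once qualifies it: "relapse and death due to a pre-existing condition, and hospitalisations for elective treatment of a pre-existing condition do not need reporting as SAEs". The same section makes the Chief Investigator's opinion on relatedness and expectedness the test for reporting to the ethics committee, and adds "The Chief Investigator must also notify the Sponsor of all SAEs".

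Section 7.1 describes the population as "10 evaluable patients with suspected cerebral glioma on previous MRI who are due to undergo surgical resection or biopsy". Section 8.1 requires a tumour of at least 2 cm and "WHO performance status 0 – 2". Section 9.3 has the investigators halt the study temporarily after an SAE judged related to dosing, and separately permits dosing to be suspended at any time on safety grounds.

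**The concern.** The three safety sections do not fit together for one kind of event: a death inside the reporting window that someone ascribes to the brain tumour. It is serious by 13.1 and inside the window of 13.2, yet 13.4 excuses it from the SAE route. Since everyone enrolled has a suspected glioma, a disease explanation is available for any death, whether or not it is the right one. The exemption operates before a form exists, while the role that judges relatedness under 13.4 comes into play on the SAE route.

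What is at stake is independent review of an early death. Patients receive a tracer that section 4.3 describes as new to glioma patients, together with gadolinium and an arterial line. If a death the same evening were put down to the tumour too readily, the text would not oblige anyone to document why, or to tell the sponsor, before the next patient is scanned.

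**Working it through.** No sample size, power or event rate enters this point, and the plan states no figure to reproduce. The check is to follow a death within 24 hours, attributed to the glioma, through the safety sections in order.

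1. **Is it an SAE?** Yes. Section 13.1 includes fatal events whatever the cause.
2. **Is it inside the window?** Yes. Section 13.2 covers the 24 hours after injection and refers to the procedures below it.
3. **Does the non-serious route catch it?** No. Section 13.3 applies to non-serious events and asks only for recording.
4. **Is the SAE form required?** On the plain reading, no. The exemption in 13.4 directly follows the form requirement and qualifies it. It is not limited to events after the 24-hour window, and it names nobody to decide or confirm the cause.
5. **Is the sponsor told?** Section 13.4 has the Chief Investigator notify the sponsor of all SAEs. If the exemption means that no form is sent, nothing expressly sets this step in motion.
6. **Is relatedness judged?** Section 13.4 gives that opinion to the Chief Investigator, but no sentence requires it for an event already exempted. The mandatory halt in 9.3 needs an SAE judged related, so the judgement may never be documented.

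No other section closes this route with a mandatory step. Section 9.2 has the study team look at safety data for trends, but in the context of withdrawing a subject. The suspension power in 9.3 is permissive. Section 11.2 provides a telephone call at 24 hours, which may well reveal a death but does not say how it is then reported.

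**Size of the exposure.** Patient-days at risk = number dosed × length of window. With 10 patients and 1 day each, 10 × 1 = 10 patient-days. This is not an upper bound: 10 is the number of evaluable patients, and section 9.2 allows extra subjects when someone is withdrawn before or after dosing. With k dosed patients replaced, the exposure is 10 + k patient-days. The documents give neither k nor a death rate. That deaths from disease in this window would be rare is an assumption, based on the single day of follow-up and the entry requirements for performance status and absence of significant co-morbidity (section 8.1).

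**The case against.** The best reply is that the exemption is narrow and the plan has other protections. Much of this stands.

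- The exemption covers deaths due to a pre-existing condition. It does not cover every death in a patient who has one. A death attributed to the tracer or a procedure stays reportable, and nothing tells staff to ascribe an unclear death to the tumour. This stands: the gap concerns wrong or uncertain attributions only.
- Section 13.2 still asks for all adverse events in the window to be reported, 13.4 still refers to all SAEs when it deals with the sponsor, and 13.2 sends reporting questions to the Chief Investigator. These sentences can be read as still covering such a death. That is a fair reading, but it conflicts with the exemption and nothing says which prevails, so the sections need reconciling either way.
- A reader might infer that the halt in 9.3 cannot be triggered. The documents do not support that. Section 9.3 requires a judgement of relatedness, not a form; suspension for safety is always open; and a death truly caused by glioma would not meet the halt criterion even if reported.
- A reader might also infer that the reference to relapse is meaningless before diagnostic surgery. It is not: the first exclusion in 8.2 bars recent systemic therapy only, so previously treated patients can enter and relapse can occur.
- Exemptions of this kind have a purpose where follow-up is long and disease deaths are common. The plan gives no reason for one in a 24-hour window.

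**Conclusion.** The point holds as a minor weakness in safety oversight. Sections 13.1, 13.2 and 13.4 are inconsistent for a death within 24 hours of injection. On the plain reading of 13.4, attribution to the tumour comes before any report and is reviewed by nobody who is named. The text does not establish that such a death would bypass the sponsor, only that it need not be notified.

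The practical likelihood is low: about one patient-day per person dosed, 10 for the planned evaluable patients and more if dosed patients are replaced. This rests on two things: reading the exemption as qualifying the form requirement just before it, and the assumption that disease deaths in the window are rare. If the second is right, the exemption saves almost no work, which is why removing it there is worthwhile. The primary endpoint, the sample size and the analyses are untouched.

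**What to change.** Amend 13.4 so that its exemption does not apply to deaths within the 24-hour reporting window. Any such death should go on the SAE form to the Chief Investigator, who records a judgement on relatedness and notifies the sponsor. This brings 13.4 into line with 13.1 and 13.2. Leave the exemptions for relapse and for elective hospitalisation as they are; the latter is needed because every participant is due for surgery or biopsy. The halt and suspension provisions in 9.3 need no change for this purpose.

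The cost is one sentence by amendment and, at most, one additional form per dosed patient, in practice a rare event.

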14. REGULATORY ISSUES

14.1 Pre-Trial Requirements

Measuring fatty acid oxidation in gliomas using ¹⁸F-FPIA Version 1.0 01/02/2018 IRAS: 228245

Treatment within this study will only start if the following pre-requisites have been fulfilled and documentation is at hand:

- Signed copy (original) of the approved protocol
- Ethics Committee (EC) approval of the protocol, consent form and information sheet
- Approval / notification of local authorities

The Investigator will hold an Investigator's File containing the relevant study documents.

14.2 General Legal Requirements

The study will be conducted in agreement with the following directives and guidelines:

- The Declaration of Helsinki (version of Edinburgh, Scotland, October 2000)
- The respective Guidelines of the European Community: Guideline for Good Clinical Practice (Note for Guidance on Good Clinical Practice / ICH E6) and Statutory Instrument 2004 No. 1031 - The Medicines for Human Use (Clinical Trials) Regulations 2004 as amended.

All clinical work conducted under this protocol will be subject to Good Clinical Practice rules. This includes an inspection by health authority representatives at any time. The Investigator agrees to the inspection of study-related records by health authority representatives and/or the sponsor.

14.3 Handling and Quality Assurance

The Chief Investigator will be responsible for the processing and quality control of the data. The handling of data, including data quality control, will comply with all applicable regulatory guidelines. All study documentation at the investigator site and sponsor site will be archived in accordance with the sponsor's quality standards.

14.4 Protection of Subjects

14.4.1 Ethics Committee

All patients will be recruited strictly according to protocol following the principles of the Declaration of Helsinki. All inclusion criteria would be satisfied before enrolling patients. The protocol and a copy of the subject information and informed consent form will be submitted to the competent EC, Health Research Authority (HRA), Sponsor and Local Research & Development departments. Written approval of the protocol and the proposed information and consent form will be obtained prior to the start of the trial.

